There was no statistical improvements noted for acute respiratory distress, however a decrease in respiratory system resistance was noted for infants with BPD during prone positioning.(9) In 2018 Zhong and colleagues randomized 79 preterm mechanically ventilated infants to supine vs prone positioning. Fraction of inspired oxygen (FiO₂), peak inspiratory pressure, mean inspiratory pressure, and duration of ventilation were significantly lower in the prone group than in the supine group (P < 0.05).(10)

There were no reports of adverse events in pediatric patients in the aforementioned studies. However in adult patients adverse effects such as pressure sores and tracheal obstruction were reported.

While the prior studies have shown temporal benefit for preterm, ventilated infants who undergo prone positioning, many are short term studies and none have assessed its impact on severity of BPD.

Objective: We aim to evaluate in this pilot study whether standardized prone positioning compared to usual positioning improves moderate to severe BPD rates as assessed at 36 weeks post conceptional age in VLBW preterm infants with BPD.

Material and methods

Study plan:

We aim to enroll and randomize infants born at less than 1500 grams at birth, who remain

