Personnel: Neonatologists [name] and [name] will be responsible for consenting families and determining randomization assignment. Bedside nurses along with respiratory therapists will be responsible for position changes and documentation of physiologic metrics and vital signs as part of the normal ICU care practice. [name] will collect study data for analysis. Nurse practitioner [name], BSN, DNP, will be responsible for assigning the primary outcome of moderate or severe BPD, at or after 36 weeks post conceptional age. She will be provided a list of study participants identified only by study number at 36 weeks post conceptional age, their respiratory support parameters and will assign the primary outcome of moderate (Grade 2) or severe (Grade 3) BPD.

Randomization: Block randomization with variable block sizes will be performed in order to ensure equal sample sizes over time. The treatment (standardized prone positioning) ratio to control (usual positioning) ratio will be 1:1. The randomization list will be generated by the study statistician and will be maintained under locked conditions. Blinding of staff is inherently not feasible as scheduled prone position changes are obvious to caretakers.

Evaluations and measures: Incidence and severity of BPD will be assessed at 36 weeks post conceptional age. As part of usual NICU care, infants, especially those on respiratory support have vital signs and other physiologic parameters recorded routinely every 3 hours,

but this may occur as frequently as every hour in the sickest infants. Enrolled infants will have physiologic data and vital signs evaluated and recorded at start of hands-on time, at the 1 hour mark after scheduled position change to prone, at the time of switch to supine, 1 hour after 2nd switch to prone position, and at the time of conclusion of study positional changes. For infants randomized to usual care, we will record similar data from a period of 3 hands-on intervals (total of 9 hours).

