We aim to record and collect the following data once weekly on the weekly anniversary of the infantâ€™s first study prone positioning and the date of randomization onto the study for those study participants who were randomized to usual care: transcutaneous CO₂ (TCO₂) if available or PCO₂ from any blood gas, SaO₂ from cardiopulmonary monitors, PaO₂ from arterial blood gases within 1 hour of positional change (if available), ventilator or other respiratory support modality settings and direction of changes within 1 hour of positional change. Specifically, percent change in inspired oxygen, change in ventilator rate (breaths per minute), tidal volume (milliliters), peak inspiratory pressure (cm H₂O), positive end expiratory pressure (cm H₂O) and the number of episodes of oxygen desaturations will be collected. Current comorbidities, most recent chest x-ray findings within a 7day interval will also be documented once weekly.

Other data: duration of time on any respiratory support (days), duration of use of endotracheal tube, non-invasive positive pressure ventilation (NIPPV) and continuous positive airway pressure (CPAP), time to FiO₂ of 21% (irrespective of type of respiratory interface), type of medications to treat BPD (use of oral, inhaled or intravenous postnatal steroids for mitigation of BPD, caffeine, diuretics daily or intermittent), presence of pulmonary hypertension as documented by echocardiogram, use of sedatives and analgesics, pharmacologic treatment of

GERD, use of inhaled nitric oxide on DOL 7 or later. Additionally, the mode of ventilation at 7 days after birth, DOL when maximal feeds achieved (total fluids of 160 milliliters per kilogram per day), DOL at which feeding by mouth was initiated and DOL at which feeds were administered by mouth only, diagnosis of plagiocephaly, and the duration of NICU stay. Demographic data of interest include gestational age at birth (weeks), maternal comorbidities, infant comorbidities, growth status (small, appropriate or large for gestational age), weight at birth (kilograms) and use of antenatal steroids.

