that patient characteristics are distributed similarly across groups. The difference between the intervention and control arms in the rate of BPD at 36 weeks post-conceptional age and other outcomes will be estimated, along with corresponding 95% confidence intervals. In exploratory analyses, the chi-square test will also be applied to assess whether the rates of BPD and other binary outcomes are significantly different between groups, and the two-sample t-test will be used compare the mean values of continuous variables measured at a specific visit. Logistic and linear regression models will also be fit to the data to adjust for any baseline characteristics that are not balanced across groups despite randomization. Weekly physiologic, ventilator and other clinical data will be obtained and analyzed using generalized linear mixed models, with the logit link for binary outcomes and the identity link for continuous outcomes, to account for the correlation in repeated measures from the same infant. Missing data will be handled by analyzing the available data as well as by multiple imputation using chained equations. All analyses will be based on the intent-to-treat approach, and results will be viewed as exploratory and hypothesis generating.

We plan to randomize a total of 60 patients 1:1 to intervention and control (N=30 per arm). Since this is a pilot trial, the goal is to obtain preliminary data on effect sizes. Therefore, formal power calculations were not performed. With 30 patients per arm, the precision, as measured by the width of the 95%CI, with which the true intervention effect (i.e., difference between groups) can be estimated is +/- 25% or better. For example, to gauge the magnitude of the primary outcome of BPD incidence and the potential benefit of standardized prone positioning, we evaluated 2019 BPD rates in our NICU. There were 107 patients described as VLBW at birth. Of those, 34 infants developed moderate to severe BPD, a rate of 31%. If the observed BPD rate is reduced to 21% in the intervention arm for a between group difference of

10%, then the corresponding width of the 95% CI for the true difference will be +/- 22%. We anticipate performing this pilot study over 2-3 years to account for yearly variations in the admission of VLBW patients.

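### Oral-feeding milestones recorded as day of life, with gestational age adjusted for only if unbalanced, carry the spread in gestational age as avoidable variance: lost precision, not bias

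*Combined protocol and SAP*

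**What the plan says.** Under Evaluations and measures, the Other data paragraph lists "DOL at which feeding by mouth was initiated and DOL at which feeds were administered by mouth only". Gestational age at birth, in weeks, is collected in the same paragraph as a demographic variable.

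The Study plan sets entry by birth weight: "We aim to enroll and randomize infants born at less than 1500 grams at birth". It also requires at least 7 days of respiratory support after birth. It states no gestational-age limit. The Randomization paragraph says "Block randomization with variable block sizes will be performed in order to ensure equal sample sizes over time" and names no stratification factor.

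Statistical Considerations gives three provisions that bear on these milestones:

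- Differences between arms in the BPD rate "and other outcomes will be estimated, along with corresponding 95% confidence intervals".
- For continuous data, "the two-sample t-test will be used compare the mean values of continuous variables measured at a specific visit".
- Covariate adjustment is conditional on what the baseline table shows: "Logistic and linear regression models will also be fit to the data to adjust for any baseline characteristics that are not balanced across groups", that is, those that differ despite randomisation.

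Gestational age is not named as a covariate for any analysis. The sample is 60 infants, 30 per arm. The stated goal is preliminary data on effect sizes, and all results are to be viewed as exploratory.

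**The concern.** If oral feeding depends largely on maturity, an infant born at 24 weeks will reach these milestones many more days after birth than one born at 30 weeks, though perhaps at a similar PCA. Day of life then mixes two things: how mature the infant was at the milestone, which positioning might affect, and how early the infant was born, which it cannot. The second is fixed before randomisation and is pure noise in the comparison of arms.

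The plan justifies 30 per arm by the width of a confidence interval, so precision is its own criterion. As written, gestational age enters the milestone analysis only if it is judged unbalanced. In most trials it would stay out, and the intervals would be wider than the collected data allow.

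**Working it through.** **The plan's own precision figure.** For 31% versus 21% with 30 per arm, 1.96 x sqrt(0.31 x 0.69/30 + 0.21 x 0.79/30) = 0.2205, which reproduces the stated +/- 22%. At 50% versus 50% the result is 25.3%, in line with the general +/- 25%. The plan gives no precision figure for the feeding milestones.

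**Inputs.** From the documents: 30 per arm, milestones in DOL, gestational age (GA) in weeks. Assumed, because the documents give none of them:

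- SD of GA: 1.5, 2.0 or 2.5 weeks
- slope b of milestone PCA on GA: 0, -0.3 or -0.5
- residual SD of milestone PCA around that line (SD_e): 1.5, 2.0 or 3.0 weeks

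**Formulas.** With PCA = a + b x GA + e and DOL/7 = PCA - GA:

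- Var(DOL/7) = (1 - b)^2 x SD_GA^2 + SD_e^2
- Var(PCA) = b^2 x SD_GA^2 + SD_e^2
- 95% half-width in days = 1.96 x 7 x sqrt(2 x Var/30)

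**Central case** (SD_GA 2.0, SD_e 2.0, b = -0.3):

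- DOL: variance 6.76 + 4 = 10.76, half-width 13.72 x sqrt(0.7173) = 11.6 days
- PCA: variance 0.36 + 4 = 4.36, half-width 13.72 x sqrt(0.2907) = 7.4 days
- Variance ratio 10.76/4.36 = 2.5
- With GA as a covariate on either scale, only SD_e^2 = 4 remains: 13.72 x sqrt(0.2667) = 7.1 days

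**Extremes of the grid:**

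| SD_GA | SD_e | b | Var DOL/7 | Var PCA | Variance ratio | Width ratio |
|---|---|---|---|---|---|---|
| 1.5 | 3.0 | 0 | 11.25 | 9.00 | 1.25 | 1.12 |
| 2.5 | 1.5 | -0.3 | 12.81 | 2.81 | 4.56 | 2.13 |

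The unadjusted DOL interval is therefore about 12% to 113% wider. Across the grid, half-widths run from 7.5 to 17.0 days for DOL and from 5.3 to 11.5 days for PCA.

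**Dependence on the slope.** The two variances are equal when (1 - b)^2 = b^2, at b = 0.5. With total SDs of 2 weeks for both GA and milestone PCA, so that the correlation equals the slope, the DOL interval is 41% wider at 0, 18% wider at +0.3 and no wider at +0.5. Above 0.5 the PCA scale is the less precise one.

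**GA as a covariate.** Subtracting GA from the response changes only the GA coefficient, by 1. The treatment estimate and its interval are then identical for DOL and PCA. Simulated fits agreed to about 1e-14.

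**Adjusting only when unbalanced.** The plan gives no rule for declaring imbalance. A p<0.05 trigger was assumed and simulated with 2,000 replicates per scenario and t quantiles. With both SDs at 2 weeks and b = 0, the trigger fired in about 5% of trials. Mean half-widths were 10.16 days for unadjusted DOL, 10.04 with conditional adjustment and 7.26 with adjustment always.

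**Bias.** In the five simulated scenarios, unadjusted DOL intervals covered the true difference 94.6% to 96.0% of the time.

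**The case against.** The strongest reply is that the documents do not fix DOL as the analysis scale. The milestones sit in a list of data to collect, and PCA can be derived at any time from GA and DOL. That is correct. A reader might also take the t-test sentence as the planned test for these milestones. It is worded for variables measured at a specific visit, which a feeding milestone is not, so it cannot carry the point. What stands is that the sentence on other outcomes covers the milestones, no step converts them to PCA, and GA enters a model only if unbalanced.

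A reader might infer that entry by birth weight alone guarantees a wide GA spread. It does not: the 7-day respiratory-support requirement may exclude more mature infants and narrow the spread. This is one reason the SDs above are only assumptions.

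A reader might infer that a chance imbalance in GA would distort the result unchecked. At SD_GA 2.0 the standard error of the GA difference is 2 x sqrt(2/30) = 0.52 weeks. A one-week gap is thus about 1.9 standard errors and would move the DOL difference by 7 x (1 - b), or 7 to 10.5 days for b from 0 to -0.5. A gap that visible could trigger the planned regression. Smaller gaps might not: half a week moves the difference by 3.5 to 5.3 days. Such shifts average to zero over randomisation and are already reflected in the wider interval. They are imprecision, not bias.

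The half-widths also assume that all 30 infants per arm reach the milestone, while the Background reports 9 deaths among 107 infants. Equal losses widen both intervals by the same factor and leave the ratio unchanged.

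Finally, scale is not the root issue, because with GA in the model the two scales coincide. This stands and shapes the fix. Duration of NICU stay and of respiratory support raise the same covariate question.

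**Conclusion.** The point holds as a low-severity, free improvement. Followed as written, the milestone comparisons would usually be unadjusted for GA and would carry its spread as avoidable variance. Under the assumed SDs and slopes, the unadjusted DOL interval is about 12-113% wider than the PCA interval, with central half-widths of 11.6 and 7.4 days. That range is illustrative, because none of its three inputs is in the documents. It shrinks with a positive slope and disappears for the PCA scale at 0.5.

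The documents do not support reading this as a biased or invalid analysis, or as a threat to the trial's main result. Coverage holds, the outcomes are exploratory in a pilot without a formal power calculation, and the primary outcome is assigned at 36 weeks PCA.

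**What to change.** In Statistical Considerations, pre-specify that the linear models for first oral feed and full oral feeds include gestational age at birth (continuous, in weeks) as a covariate regardless of observed balance. Report the between-arm difference in days with its 95% confidence interval. This is the more robust form: it removes the linear contribution of GA whatever the slope, and gives the same answer for DOL and PCA.

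At the least, analyse PCA at the milestone, derived as gestational age + DOL/7, and keep DOL as description.

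The cost is one sentence and one model term or derived variable; both inputs are already collected. The covariate uses one degree of freedom. With a zero slope and both SDs at 2 weeks, the mean simulated half-width rose only from 7.20 days (unadjusted PCA) to 7.26.

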on positive pressure support for at least 7 days after birth AND/OR on any other respiratory device such as nasal cannula with flow rates greater than 2LPM receiving supplemental oxygen of greater than 21% for at least 7 days after birth. Positive pressure for the purposes of this study is defined a nasal cannula delivering a flow of 2 LPM or higher, continuous positive airway pressure (CPAP), non-invasive positive pressure ventilation or non-invasive mechanical ventilation (NIPPV/NIMV), as well infants who are intubated or have a tracheostomy for oxygenation and ventilation related to their lung disease, irrespective of the mode of ventilation. We will exclude infants who were previously on room air without a respiratory device who were intubated for the purposes of surgery and were not receiving respiratory support as defined above prior, those intubated for other airway issues such as tracheal stenosis, broncho- or tracheomalacia, etc and not for the management of BPD. Additional patients to be excluded include those with suspected or proven genetic or other major congenital anomalies that may impact cardiac and lung function including cardiac and lung anomalies, as well as those at the time of enrollment who require surgeries that will impact their ability to be placed in prone positioning (eg gastroschisis, omphalocele, etc).

Patients meeting the aforementioned criteria will be assigned to 1. usual care in which positioning and duration in each position is random per usual nursing routine OR 2. Receive standardized scheduled daily prone positioning starting on day of life 7. As part of normal developmental care, most infants are evaluated and have care rendered (touch-time), if stable, and repositioned at set three-hour intervals to permit uninterrupted sleep and/or rest. The hands-off interval will be maintained throughout the study interval. Infants randomized to the standardized scheduled daily prone positioning will be placed in prone body position for a total of 6 hours daily, that is prone position for 3 hours, followed

by supine positioning for 3 hrs, then placed in prone position for another 3-hour interval. Standardized daily positioning will occur for randomized patients until 36 weeks or discharge whichever is first. If needed, position aids, which are part of the normal care routine in our ICU, may be used to facilitate maintenance of prone or supine positioning.

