Weekly physiologic and ventilatory data will be collected until the infant reaches 36 weeks postconceptional age or discharge from the NICU, or is on 21% FiO₂, i.e. O_2 room air, without any respiratory interface, whichever is earlier. For the purposes of our study, the primary outcome of moderate (Grade 2) to severe (Grade 3) BPD will be clinically defined and assigned at 36 weeks PCA based on the 2019 study by the Eunice Kennedy Shriver National Institute of Child Health and Human Development Neonatal Research Network which assessed the definition of BPD that best predicted early childhood morbidity.⁽¹¹⁾ The definitions are as follows:

Severe (Grade 3) BPD: If an infant requires invasive positive pressure ventilation via an endotracheal or tracheostomy irrespective of the amount of FiO₂.

Moderate (Grade 2) BPD: If an infant requires nCPAP, NIPPV, HFNC, or NC > 2 liters per minute flow and receiving $\geq 21\%$ FiO₂.

Infants receiving NC 2 liters per minute or lower flow rates, irrespective of the FiO₂ received, will be considered as having mild (Grade 1) BPD and will not be assigned the primary outcome.

Statistical Considerations: Demographic and clinical variables assessed at baseline will initially be summarized by intervention arm using standard descriptive statistics to confirm

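### Weekly records run from about day 7 to a fixed postconceptional age, so later study weeks hold only less mature infants; gestational age at birth should be a prespecified covariate in the weekly analyses

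*Combined protocol and SAP*

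**What the plan says.** Eligibility is set by birth weight: "We aim to enroll and randomize infants born at less than 1500 grams at birth" (Study plan). No limit on gestational age is stated. The intervention arm is to "Receive standardized scheduled daily prone positioning starting on day of life 7".

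Under Evaluations and measures, weekly data are taken on the weekly anniversary of the infant's "first study prone positioning and the date of randomization onto the study for those study participants who were randomized to usual care". The end of collection is a fixed age or an event: "Weekly physiologic and ventilatory data will be collected until the infant reaches 36 weeks postconceptional age or discharge from the NICU", or room air "without any respiratory interface, whichever is earlier".

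Under Statistical Considerations, "the two-sample t-test will be used compare the mean values of continuous variables measured at a specific visit". The visit is not named. Weekly data also go into generalized linear mixed models, for which neither a time variable nor covariates are listed. Logistic and linear regression will adjust for baseline characteristics that turn out unbalanced. GA will be available: "Demographic data of interest include gestational age at birth (weeks"). All results are labelled exploratory.

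**The concern.** The clock starts shortly after birth and stops at a fixed PCA, so the length of the weekly series is set largely by how early the infant was born. Each later study week drops the most mature infants still in the series. This would happen even if no infant reached room air or went home before 36 weeks.

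There are two consequences. A comparison at one late week rests on fewer infants, and they are less mature than the trial population. A sequence of raw weekly means mixes change within infants with change in who is measured. Respiratory measures can be expected to depend strongly on GA, so leaving GA out also puts its spread into the error term of every weekly comparison. Since the stated goal of the pilot is preliminary data on effect sizes, precision and a clear population for each estimate matter.

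**Working it through.** **The plan's own figure.** For 31% against 21% with 30 per arm: 1.96 x sqrt(0.31 x 0.69/30 + 0.21 x 0.79/30) = 1.96 x 0.1125 = 0.2205. The stated +/-22% is reproduced. It concerns the primary outcome at 36 weeks PCA and does not depend on what follows.

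**Number of weekly records.** PCA at the start is GA + 1, so possible records = 36 - (GA + 1) = 35 - GA.

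| GA at birth (weeks) | 24 | 26 | 28 | 30 | 32 |
|---|---|---|---|---|---|
| Weekly records possible | 11 | 9 | 7 | 5 | 3 |

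Study week w can include only infants with GA of at most 35 - w.

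**How fast the sample thins.** The documents give no GA distribution, so this part is assumption: GA normal with SD 2, truncated to 22-34 weeks, and the 36-week stop only. Infants out of 60 still under collection:

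| Study week | Median GA 26 | Median GA 28 | Median GA 30 |
|---|---|---|---|
| 4 | 60 | 56 | 42 |
| 6 | 56 | 42 | 19 |
| 7 | 50 | 30 | 10 |
| 8 | 41 | 18 | 4 |
| 9 | 29 | 9 | 1 |

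Half remain at about week 35 minus median GA: week 9, 7 or 5.

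**Precision of a single-visit t-test.** The 95% half-width in SD units is t x sqrt(2/n). With 30 per arm it is 0.52; with 15 per arm, 0.75. The difference detectable with 80% power goes from 0.72 to 1.02 SD.

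**Raw means by week (assumed values).** Let GA be spread evenly over 24-33 weeks and FiO2 at week k be 23 + 2 x max(32 - GA, 0) - k, so every infant falls 1 point a week.

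- Week 4 (GA 24-31, mean 27.5): 23 + 9 - 4 = 28.
- Week 7 (GA 24-28, mean 26): 23 + 12 - 7 = 28.
- Week 9 (GA 24-26, mean 25): 23 + 14 - 9 = 28.

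The raw mean is flat although every infant improves. The illustration has no treatment term, so it says nothing about a difference between arms.

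**Value of adjusting for GA (same mix; assumed between-infant SD 4 and residual SD 3).** The GA term takes the values 16, 14, ..., 2, 0, 0, with variance 81.6 - 7.2^2 = 29.76. The mean of 1/(number of records) over 2 to 11 records is 0.202, so averaged residual variance is 9 x 0.202 = 1.82. For an arm effect common to all weeks:

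- GA left out: sqrt(2/30 x (29.76 + 16 + 1.82)) = 1.78.
- GA removed: sqrt(2/30 x (16 + 1.82)) = 1.09.

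Simulating the mixed model under these assumptions gave about 1.76 and 1.09, with no bias either way.

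For one week alone, without borrowing from other weeks, the gain is smaller and shrinks with time as the GA range narrows:

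- Week 1 (30 per arm): sqrt(2/30 x (29.76 + 16 + 9)) = 1.91 against sqrt(2/30 x 25) = 1.29.
- Week 7 (15 per arm, GA variance 8): sqrt(2/15 x (8 + 16 + 9)) = 2.10 against sqrt(2/15 x 25) = 1.83.

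**The case against.** A reader might infer three stronger points. The documents support none of them.

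*That half the sample is lost by about week 7.* This needs a median GA near 28 weeks, which is not stated. At week 7, about 50 or about 10 of 60 would remain if the median were 26 or 30. The loss also applies only to a single-visit analysis; the mixed models use every available record.

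*That the comparison between arms is biased.* GA is fixed before randomisation, so this loss is balanced between arms in expectation. The stops at discharge and at room air are different: they happen after randomisation and could differ by arm. They are a separate matter, and adjusting for GA does not cure them. If they removed an assumed further 5-10% a week (SD 2), the first week with no more than half under collection would be 8-6, 7-5 or 5-4 for median GA 26, 28 or 30.

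*That PCA should replace study week.* The plan names no time axis, so it cannot be said to have chosen the wrong one. Time since randomisation is a legitimate axis for an intervention effect. On the even 24-33 week mix, at 35 weeks PCA an infant born at 24 weeks has had 35 - 25 = 10 weeks of study positioning and one born at 33 weeks has had 35 - 34 = 1. The thin weeks would also move to the start: at 32 weeks PCA, coverage is 70-80%, depending on whether the first record falls at entry or a week later.

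It is also fair to say that the analyses are exploratory and that regression adjustment is already allowed. What remains is that this adjustment depends on observed imbalance. A strong prognostic variable adds noise even when it is balanced.

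**Conclusion.** The point holds as one of precision and interpretation. The tie between GA and the number of weekly records follows from the documents. The week at which half the sample remains is an assumption with a range of about 5 to 9 from the 36-week stop alone. In the illustration, adjusting for GA shortens the standard error of a common arm effect by about 38% (1 - 1.09/1.76); at week 7 taken alone, by about 13% (1 - 1.83/2.10). These gains rest on the assumed GA mix, slope and SDs. They apply to continuous outcomes and would be smaller if the GA gradient were weaker. The primary outcome at 36 weeks PCA and the +/-22% figure stand as they are.

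**What to change.** In Statistical Considerations:

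1. Include gestational age at birth as a covariate in all weekly mixed models, whatever the observed balance.
2. Take visit-specific arm differences, with 95% confidence intervals, from that GA-adjusted model instead of the unadjusted two-sample t-test. State that the time axis is study week and name the weeks of interest.
3. Report the number of infants contributing at each week, by arm.
4. If wanted, add a display by PCA as a sensitivity presentation alongside study week.

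The cost is wording only. GA is already listed for collection, and neither the schedule nor the sample size changes. The model spends one parameter on a linear GA term, and its form should be stated in advance. For binary weekly outcomes with the logit link, the adjusted odds ratio is conditional on GA and should be reported as such.

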Both infants randomized to standardized prone positioning and usual positioning will have a bedside card card identifying that the infant is a study participant and will serve as a way to document the number of times any infant enrolled in the study is placed in prone positioning even if not randomized to standardized prone positioning. The bedside card also facilitates the infantâ€™s nurse being aware of the time of day for prone into supine position change for those who are randomized to prone positioning. On the weekly anniversary of the infantâ€™s first placement in prone position for the study, physiologic and clinical data will be retrieved.

Risk/Benefit: anticipated medical, social, psychological, and/or legal risks are minimal; however uncommon risks to be being placed prone may include movement or dislodgement of a breathing tube or of an intravenous (IV) catheter. These uncommon risks will be minimized by staff paying strict attention to the positions of these devices during movement from prone to supine position and vice versa. Additionally, documentation of the positions of these devices is routine and will permit tracking of change in position of the devices. Potential benefits include a decrease in the severity and occurrence of moderate to severe BPD, a common condition of the lung related to premature birth.

Data storage and maintenance of confidentiality: Data will be reviewed and retrieved from the electronic medical record into a computerized study data form kept on a password protected computer in a locked office. Only the 2 study personnel, [name] and [name] will access study files to check or edit data. Consent forms will also be kept in a locked office. The study database will be permanently deleted and paper data collection tools will be shredded. Subjects will not be video or audiotaped during this study.

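### If twins or triplets are enrolled, the between-arm analyses treat them as independent, and the plan has neither a sibling randomisation rule nor a family identifier; the effect is modest and its direction depends on allocation

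*Combined protocol and SAP*

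**What the plan says.** Eligibility is set at the level of the infant: "We aim to enroll and randomize infants born at less than 1500 grams at birth" (Study plan). The exclusions cover intubation only for surgery, airway problems other than BPD, surgery that prevents prone positioning, and anomalies ("Additional patients to be excluded include those with suspected or proven genetic or other major congenital anomalies that may impact cardiac and lung function"). Multiple birth is not among them, and twins, triplets and siblings are mentioned nowhere.

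Under Randomization: "Block randomization with variable block sizes will be performed in order to ensure equal sample sizes over time". The ratio is 1:1, with 60 infants and 30 per arm. No block sizes are given and there is no rule for siblings.

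Under Statistical Considerations, differences between arms in BPD and other outcomes "will be estimated, along with corresponding 95% confidence intervals". Chi-square tests, two-sample t-tests and logistic and linear regressions are added. None carries a family term or a clustered variance. The mixed models for weekly data are chosen "to account for the correlation in repeated measures from the same infant" and for no other source of correlation.

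The demographic items listed under Evaluations and measures are "gestational age at birth (weeks), maternal comorbidities, infant comorbidities, growth status", followed by birth weight and antenatal steroid use. Multiple-birth status and a sibling link are not listed.

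**The concern.** Siblings from one pregnancy share a mother, antenatal steroid exposure, gestational age and unit. Their BPD status, days on support and length of stay are therefore likely to be correlated. An analysis that counts them as independent gets the variance of the between-arm difference wrong. It does not bias the estimated difference itself.

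This bears on the pilot because its sample size is justified only by precision: a 95% interval of about 22 points either side in the worked example, and 25 points or better in general. Both figures assume 60 independent infants. The sign of the error depends on whether siblings land in the same arm or in opposite arms, and the plan leaves that unstated.

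**Working it through.** **Inputs from the plan.** 30 infants per arm, 95% confidence, BPD rates of 31% and 21%.

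**Inputs assumed, because the documents give none.** 6 to 12 twin pairs (20 to 40% of the 60 infants); within-pair correlation ρ of the binary outcome of 0.3 to 0.7; block sizes of 2 and 4, with 4 and 6 as an alternative, each size equally likely.

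**Step 1: the plan's own figure.** Treating all infants as independent:

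1.96 × √[(0.31 × 0.69 + 0.21 × 0.79)/30] = 1.96 × √(0.3798/30) = 0.2205, or 22.05 points.

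This reproduces the stated 22. At 50% in both arms the half-width is 25.3 points, which matches the general statement of 25.

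**Step 2: effect of twin pairs.** Let S be the number of pairs in the same arm and O the number in opposite arms. With a common outcome variance σ²,

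Var(difference) = (1/900) × [60σ² + 2ρσ²(S − O)],

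so true variance / naive variance = 1 + ρ(S − O)/30. Same-arm pairs add variance and opposite-arm pairs remove it.

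**Step 3: how often separately randomised siblings are split.** Siblings consented in the same DOL 5 to 7 window would probably take adjacent places on the list.

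- Blocks of 2 and 4: (1 + 3 × 2/3 + 2 × 1/2)/6 = 0.67. On average S − O = −k/3 for k pairs.
- Blocks of 4 and 6: (3 × 2/3 + 5 × 3/5 + 2 × 1/2)/10 = 0.60. On average S − O = −k/5.

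**Step 4: results at the two ends of the assumed range.** Each cell gives the true/naive SE ratio and the correct half-width in points, against 22.05 naive.

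| Allocation | S − O | 6 pairs, ρ = 0.3 | 12 pairs, ρ = 0.7 |
|---|---|---|---|
| All pairs share an arm | +k | 1.030; 22.70 | 1.131; 24.95 |
| Separate, blocks 2 and 4 (average) | −k/3 | 0.990; 21.83 | 0.952; 21.00 |
| Separate, blocks 4 and 6 (average) | −k/5 | 0.994; 21.92 | 0.972; 21.43 |
| All pairs split | −k | 0.970; 21.38 | 0.849; 18.71 |

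For example, 12 pairs sharing arms at ρ = 0.7 give √(1 + 0.7 × 12/30) = √1.28 = 1.131. With blocks of 2 and 4 the naive interval is 1/0.990 − 1 = 1.0% to 1/0.952 − 1 = 5.0% too wide. With blocks of 4 and 6 it is 0.6 to 2.9% too wide. Under simple randomisation S − O averages about zero, and so does the error.

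**Step 5: coverage by simulation.** With 30% of infants in twin pairs, a latent correlation of 0.6 (about 0.39 on the binary scale) and blocks of 4 and 6, coverage of the naive 95% interval was:

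- no siblings: 94.3%
- siblings randomised separately: 94.3%
- siblings kept together: 92.9%
- siblings always split: 95.5%

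A second simulation used 6 to 12 pairs, latent correlation 0.6 to 0.85 and blocks of 2 and 4. Naive coverage was about 92 to 94% with siblings kept together and close to nominal with separate randomisation. A family-clustered standard error with a small-sample correction gave about 94.4 to 95.3% in both cases.

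**The case against.** The strongest reply is that this hardly matters. If siblings are randomised separately, which is the natural reading of a plan that speaks only of infants and patients, the correct half-width is 21.0 to 21.8 points instead of 22.05 (blocks of 2 and 4). The error is conservative. The point estimate is unaffected, there is no decision threshold, and all results are labelled exploratory. The upper values of ρ are also high: 0.5 to 0.7 on the binary scale implies a latent correlation of about 0.74 to 0.90. All of this stands, and it limits the weight of the point. It does not make the independence assumption right, and the plan does not rule out keeping siblings together, where the error is no longer conservative.

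Three stronger readings are tempting, and the documents do not support them.

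- A reader might infer that the intervals are too narrow. That holds only if siblings mostly share an arm, and nothing in the plan provides for that.
- A reader might infer that the data are certain to be correlated across infants. That depends on siblings enrolling. Both must weigh under 1500 g, both must still need qualifying support, and consent must be given for both. The documents give no multiple-birth rate, and separate randomisation is itself inferred from silence.
- A reader might infer from the data storage section ("The study database will be permanently deleted and paper data collection tools will be shredded") that the correlation could never be handled later. No deletion date is given, and nothing says deletion precedes analysis. Infants are found and their data retrieved through the electronic medical record, so sibling links can be recovered while the study runs.

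**Conclusion.** The point holds as a minor one, conditional on siblings being enrolled. In that case the planned between-arm intervals, tests and regressions misstate their uncertainty, and the weekly mixed models address correlation only within an infant. On the assumed 6 to 12 pairs and ρ of 0.3 to 0.7, the naive interval averages about 1 to 5% too wide with separate randomisation in blocks of 2 and 4 (less in larger blocks). If every pair shares an arm, the true SE is about 3 to 13% larger than the naive one. These figures treat all sets as twins and use a common variance in both arms. The separate-randomisation figures are averages, and the realised S − O in one small trial may differ. The case for acting is that a clustered variance is close to nominal whichever way siblings fall, at almost no cost.

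**What to change.** - **Evaluations and measures:** add a coded multiple-birth set (family) number to the baseline data.
- **Randomization:** state whether siblings are randomised separately or together, since this sets the direction of the error.
- **Statistical Considerations:** compute the BPD rate difference and the other between-arm comparisons with family-clustered standard errors and a small-sample correction, for example GEE with an independence working correlation. For the weekly data, use a family-clustered variance. Keep a family random effect as a sensitivity analysis, only if it can be estimated; with 60 infants and few pairs, a logit model with that extra level may be unstable.

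The cost is one field, one sentence and a change of variance estimator. Sample size, procedures and care are unchanged. The drawback is slightly less stable standard errors if very few sibling sets enrol. A side benefit is that the pilot could report the number of sibling sets and their outcome correlation for the design of a later trial.
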